6.1.2 Protocol deviations

A listing of all protocol deviations will be provided based on the ITT and presented by IMP, indicating if PD is COVID-19 related or not.

6.1.3 Medical history

Any medical condition reported on the Medical History form of the eCRF will be coded based on MedDRA dictionary. Medical History will be summarized by IMP and overall, by Primary System Organ Class (PSOC) and preferred term (PT) in the ITT. A participant will be counted only once for each PT. If a participant reports multiple PTs within the same PSOC then the participant will be counted only once for this PSOC. The summary will present the results alphabetically by PSOC and within each PSOC by decreasing frequency of the PT based on the active comparator. Summaries will be repeated by pre and during the COVID-19 era based on the enrollment date.

A by-participant listing will be provided based on the ITT population. IMNM medical history will be listed separately in ITT as it is part of the baseline clinical characteristic.

6.1.4 Prior/concomitant Medications

6.1.4.1 Prior and Concomitant Medications (non – IMNM related)

Prior and concomitant medications (prescriptions or over-the-counter medications) as recorded in the eCRF will be summarized on tables overall by IMPs in SS.

A non – IMNM related medication is defined by the “indication” value on the Prior and Concomitant Medication eCRF form not equal to “Therapy for IMNM”.

Medications will be classified as follows based on imputed start and stop dates / times as outlined in Section 5.1.1.8.

- **Past** medications will include any medications that started and stopped before the first administration of study drug.
- **Prior** medications will include any medications that started before the first administration of study drug.
- **Baseline** medications will include any medications that started prior to dosing and continued after (classified as prior and concomitant medications).
- **Concomitant** medications will include any medications that have been taken at least once after the first administration of study drug during the Main or the Extension Period.
- **Concomitant Only** medications will include any medication that started after the first administration of study drug and continues during the Main or the Extension Period. Any medication with a start date on the first dosing date and time unknown, will be assumed to be concomitant only.

Medications will be presented in alphabetical order by Anatomical Main Group (ATC Level 1), then by Pharmacological Subgroup (ATC level 3) and finally by decreasing frequency of PT within Zilucoplan group. In the case of ties, sort these alphabetically within the Zilucoplan. Summaries will include the overall number and percentage of participants receiving at least one treatment of a PT.

6.1.4.2 Prior and concomitant Medications (IMNM related)

IMNM specific medication will be presented separately from the other prior and concomitant medications (for both tables and listings). An IMNM specific medication is defined by the “indication” value on the Prior and Concomitant Medication eCRF form =“Therapy for IMNM”.

The following tables summarizing the IMNM medications received will be created based on the SS:

- **Past IMNM** medications will include any IMNM medication that started and stopped before the first administration of study drug.
- **Prior IMNM** medications will include any IMNM medication that started before the first administration of study drug.
- **Baseline IMNM** medications will include any IMNM medication that started prior to dosing and continued after (classified as prior and concomitant IMNM medications).
- **Concomitant IMNM** medications will include any IMNM medication that have been taken at least once after the first administration of study drug during the Main or the Extension Period.

Where an IMNM medication start date is partially or fully missing, and it is unclear as to whether the medication is prior or taken at baseline, it will be assumed that it is taken at baseline. Of note, an IMNM medication may be considered in both of these categories.

- Additionally, the number and percentage of participants who have ever received one or more of the IMNM specific medications presented below will be summarized accordingly (eCRF form = “IMNM Treatment History”:Prednisone for IMNM (yes/no)

- Azathioprine for IMNM (yes/no)
- Mycophenolate mofetil for IMNM (yes/no)
- Cyclosporine for IMNM (yes/no)
- Cyclophosphamide for IMNM (yes/no)
- Methotrexate for IMNM (yes/no)
- Tacrolimus for IMNM (yes/no)
- Rituximab for IMNM (yes/no) and number of cycles the past 24 months (continuous)
- Plasma Exchange for IMNM (yes/no) and number of cycles the past 24 months (continuous)
- IVIG for IMNM (yes/no) and number of cycles the past 24 months (continuous)
- scIG for IMNM (yes/no) and number of cycles the past 24 months (continuous)
- Other (yes/no)

6.1.5 Data derivation rules

6.1.5.1 Triple timed up and go test

The triple timed up and go test (3TUG) is a non-invasive and reproducible measure, which measures clinically important muscle weakness that impairs participant's ability to walk, climb stairs and stand up from a chair. The test will only be performed in participants who are ambulatory. The 3TUG test involves the participant getting up from a seated position in a chair, walking at their normal pace for 3 meters, turning around, walking back to the chair, and sitting down. This sequence is repeated 3 times without rest. Sites will record each lap time rounded to the nearest second, and the 3TUG time is the average of the 3 lap times. The average of the 3 lap times will be calculated to the nearest tenth place (Sanders, et al. 2018). If 2 or more of the lap times are missing, the 3TUG time will be set to missing.

6.1.5.2 Proximal Manual Muscle Testing

The proximal manual muscle testing (MMT) assesses muscle strength using manual muscle testing in 7 muscle groups. A zero to 10-point scale based on standard MMT grades will be used of 7 proximal, distal, and axial muscles (Kendall et al. 1993; Rider, Koziol, et al. 2010).

The 7 muscle groups are:

1. Trapezius
2. Deltoid middle
3. Biceps brachii
4. Gluteus maximus
5. Gluteus medius
6. Iliopsoas

7. Quadriceps.

The total score is the sum of the 7 muscle group scores with a range of 0–140 (i.e., each of the 7 muscle groups are scored on the left and right sides on a 0–10 point scale) with a higher score indicating higher muscle strength. If any of the individual items are missing the total score will be set to missing.

6.1.5.3 Physician Global Activity Visual Analogue Scale

The Physician Global Activity visual analogue scale (VAS) score, measures the global evaluation by the treating physician of the overall disease activity of the patient at the time of assessment using a 10 cm visual analogue scale (with a lower score indicating less disease activity and a higher score indicating greater disease activity) and a 0-4 point disease activity scale with 0=none and 4=extremely severe activity (Rider, Werth, et al. 2011). The VAS score will be the number of centimeters rounded to the nearest tenths place.

6.1.5.4 Patient Global Activity Visual Analogue Scale

The Patient Global Activity VAS score measures the global evaluation by the patient of the patient's overall disease activity at the time of assessment using a 10 cm visual analogue scale with a lower score indicating less disease activity and a higher score indicating greater disease activity (Rider, Werth, et al. 2011). The score will be the number of centimeters rounded to the nearest tenths place.

6.1.5.5 Health Assessment Questionnaire (HAQ)

The HAQ is a participant related outcome measure that assesses physical function.

There are 8 sections:

1. Dressing and Grooming
2. Arising
3. Eating
4. Walking
5. Hygiene
6. Reach
7. Grip
8. Activities

There are 2 or 3 questions for each section. Scoring within each section is based on the following response scales:

- Without ANY difficulty = 0
- With SOME difficulty = 1

- With MUCH difficulty =2
- UNABLE to do =3
- Answer Missing
- Answer Ambiguous

For each of the 8 sections, the score given to that section is the worst score within the section, i.e. if one question is scored 1 and another 2, then the score for the section is 2.

In addition, if an aide or device is used or if help is required from another individual, then the minimum score for that section is 2 (note: questions regarding aids or devices are requested after the Walking and Activities items).

If the section score is already 2 or more then no modification is made.

If a component question is left blank (i.e., “Answer Missing”) or the response is too ambiguous (i.e., “Answer Ambiguous”) to assign a score, then the score for that category is determined by the remaining completed question(s).

A HAQ overall score is calculated using by summing the 8 scores (i.e., from the 8 sections) and dividing by 8. In the event that one section is not completed by a subject, the summed score would be divided by 7. If more than one section is not completed the summed score would be set to missing.

6.1.5.6 Myositis Disease Activity Assessment Tool (MDAAT)

The MDAAT measures the degree of disease activity of extra-muscular organ systems and muscle. This is a combined tool that includes the myositis disease activity assessment visual analogue scales (MYOACT), which is a series of physician's assessments of disease activity of various organ systems modified from the Vasculitis Activity Index (Whiting-O'Keefe, Stone and Hellmann 1999), and the Myositis Intention to Treat Activity Index (MITAX).

The following ten MDAAT 0-10 VAS Scores will be summarized with descriptive statistics for each IMP:

1. Constitutional Disease Activity
2. Cutaneous Disease Activity
3. Skeletal Disease Activity
4. Gastrointestinal Disease Activity
5. Pulmonary Disease Activity
6. Cardiovascular Disease Activity
7. Other Disease Activity
8. Extramuscular Disease Activity (note: this is the secondary efficacy endpoint: MDAAT Score).
9. Muscle Disease Activity

10. Global Disease Activity

The following MDDAAT items are scored on a 0 - 4 scale (or NA), based on worsening or improvement in specific clinical features, as described below.

- 0 = Not present in the last 4 weeks
- 1 = Improving - clinically significant improvement in the last 4 weeks compared to the previous 4 weeks
- 2= The same - manifestations that have been present for the last 4 weeks without significant improvement or deterioration compared to the previous 4 weeks
- 3= Worse - clinically significant deterioration over the last 4 weeks compared to the previous 4 weeks
- 4= New - in the last 4 weeks (compared to the previous 4 weeks)
- NA = Cannot be assessed

The following are the set of MDAAT items scored using this 0-4 (NA) scale:

- Pyrexia – documented fever > 38o Celsius
- Weight loss – unintentional > 5%
- Fatigue / malaise / lethargy
- Cutaneous ulceration
- Erythroderma
- Panniculitis
- Erythematous rashes: **a. with secondary changes (e.g. accompanied by erosions, vesiculobullous change or necrosis)**
- Erythematous rashes: Alopecia: **b. Focal, patchy with erythema**
- Heliotrope rash
- Gottron's papules /sign
- Periungual capillary changes
- Alopecia: **a. Diffuse hair loss**
- Alopecia: **b. Focal, patchy with erythema**
- Mechanics hands
- Arthritis: **a. Severe active polyarthritis**
- Arthritis: **b. Moderately active arthritis**
- Arthritis: **c. Mild arthritis**
- Arthralgia Dysphagia: **a. Moderate / severe dysphagia**
- Dysphagia: **b. Mild dysphagia**

- Abdominal pain related to the myositis disease process: **a. Severe**
- Abdominal pain related to the myositis disease process: **b. Moderate**
- Abdominal pain related to the myositis disease process: **c. Mild**
- Respiratory muscle weakness without interstitial lung disease (ILD): **a. Dyspnea at rest**
- Respiratory muscle weakness without interstitial lung disease (ILD): **b. Dyspnea on exertion**
- Active reversible ILD (i.e. not just ventilatory abnormalities due to pulmonary fibrosis): **a. Dyspnea or cough due to ILD**
- Active reversible ILD (i.e. not just ventilatory abnormalities due to pulmonary fibrosis): **b. Parenchymal abnormalities on chest x-ray or high resolution CT scan (HRCT) and / or ground glass shadowing on HRCT**
- Active reversible ILD (i.e. not just ventilatory abnormalities due to pulmonary fibrosis): **c. Pulmonary Function Tests: > 10% change in FVC OR > 15% change in DLCO**
- Dysphonia: **a. Moderate to severe**
- Dysphonia: **b. Mild**
- Pericarditis
- Myocarditis
- Arrhythmia: **a. Severe arrhythmia**
- Arrhythmia: **b. Other arrhythmia, except sinus tachycardia**
- Sinus tachycardia
- Other Myositis: **a. Severe muscle inflammation**
- Myositis: **b. Moderate muscle inflammation**
- Myositis: **c. Mild muscle inflammation**
- Myalgia

6.1.5.7 ACR/EULAR Response Criteria

The American College of Rheumatology/European League Against Rheumatism (ACR/EULAR) scale was created to develop a response criterion for patients with myopathy. The scale utilizes a conjoint analysis-based continuous model using absolute percent change in core set measures (physician, patient, and MDAAT; muscle strength; Health Assessment Questionnaire; and muscle enzyme levels). A total improvement score (range 0-100) is determined by summing scores for each core set measure and comparing improvement in each respective core set measure. Thresholds for minimal, moderate, and major improvement are ≥ 20 , ≥ 40 , and ≥ 60 points in the total improvement score (Aggarwal, et al. 2017). The total improvement score will be calculated based on the core set measures as recorded in the eCRF and from central laboratory results as defined below in the following table.

Table 6–1: ACR/EULAR Response Criteria

Six Item with Improvement Score Scales			
1: Physician global activity	Improvement Score	4: Health Assessment Questionnaire	Improvement Score
From the Physician Global Activity Visual Analogue Scale		From the Health Assessment Questionnaire	
Worsening to 5% improvement	0	Worsening to 5% improvement	0
>5–15% improvement	7.5	>5–15% improvement	5
>15–25% improvement	15	>15–25% improvement	7.5
>25–40% improvement	17.5	>25–40% improvement	7.5
>40% improvement	20	>40% improvement	10
2: Patient global activity		5: Enzyme^a (most abnormal)	
From the Patient Global Activity VAS		From the clinical laboratory data	
Worsening to 5% improvement	0	Worsening to 5% improvement	0
>5–15% improvement	2.5	>5–15% improvement	2.5
>15–25% improvement	5	>15–25% improvement	5
>25–40% improvement	7.5	>25–40% improvement	7.5
>40% improvement	10	>40% improvement	7.5
3: Manual muscle testing		6: Extramuscular Disease Activity	
From the Proximal Manual Muscle Testing		From the Extramuscular Disease Activity VAS component of the MDAAT	
Worsening to 2% improvement	0	Worsening to 5% improvement	0
>2–10% improvement	10	>5–15% improvement	7.5
>10–20% improvement	20	>15–25% improvement	12.5
>20–30% improvement	27.5	>25–40% improvement	15
>30% improvement	32.5	>40% improvement	20

Note: this table is from Table 3 in Aggarwal, et al. (2017).

[figure not shown]
^a For muscle enzymes, the most abnormal serum muscle enzyme value at baseline (creatinine kinase, aldolase, alanine transaminase, aspartate aminotransferase, lactate dehydrogenase) is used to determine % improvement. Most abnormal will be defined as enzyme with the highest % above the ULN.

The total improvement score is the sum of all 6 improvement scores associated with the change in each core set measure. The score is between 0 and 100 corresponds to the degree of improvement, with higher scores corresponding to a greater degree of improvement.

A total improvement score of ≥ 20 represents minimal improvement, a score of ≥ 40 represents moderate improvement, and a score of ≥ 60 represents major improvement.

6.1.5.8 FACIT-Fatigue Scale

The Functional Assessment of Chronic Illness Therapy-Fatigue (FACIT-Fatigue) Scale is a 13-item, easy to administer tool that measures an individual's level of fatigue during their usual daily activities over the preceding week. The level of fatigue is measured on a five point ordinal scale (4 = not at all fatigued to 0 = very much fatigued) (Webster, Cella and Yost 2003). The items of the FACIT-Fatigue Scale are given in the table below.

Note that for the analyses, FACIT values coded as “ambiguous” are mapped to “missing” category.

6.1.6 AEs of Special Interest

Not applicable.

6.1.7 Markedly Abnormal (MA) Criteria for Safety Endpoints

Criteria listed in [Table 6-3](#) will be applied for the determination of MA values in laboratory parameters. They are based on the Common Terminology Criteria for Adverse Events (CTCAE) Version 5, November 17, 2017. The MA criterion is defined as the incidence of at least Grade 3 CTCAE, unless otherwise noted.

If both high and low criteria are shown for a parameter, then criteria should be summarized separately in tabular summaries.

Table 6-3: CTCAE v5.0 grades for laboratory assessments to be analyzed

Parameter	Unit (conventional)	Unit (Standard)	Marked Abnormality Criteria
Hemoglobin	g/dL	g/L	< 8.0 g/dL; <80g/L
WBC (Leukocytes)	10 ⁹ /L	10 ⁹ /L	Low: <2.0 x 10 ⁹ /L; High: >100 x 10 ⁹ /L
Lymphocytes Absolute	10 ⁹ /L	10 ⁹ /L	Low: <0.5 x 10 ⁹ /L High: >20 x 10 ⁹ /L
Neutrophils Absolute	10 ⁹ /L	10 ⁹ /L	<1.0 x 10 ⁹ /L
Platelets	10 ⁹ /L	10 ⁹ /L	<50.0 x 10 ⁹ /L
AST	U/L	U/L	>5.0xULN if Baseline value is normal; > 5.0x Baseline value if Baseline is abnormal
ALT	U/L	U/L	>5.0xULN if Baseline value is normal; > 5.0x Baseline value if Baseline is abnormal
ALP	U/L	U/L	5.0xULN if Baseline value is normal; > 5.0x Baseline value if Baseline is abnormal
γ-GT	U/L	U/L	>5.0xULN if Baseline value is normal; > 5.0x Baseline value if Baseline is abnormal
TBL	mg/dL	μmol/L	>3.0xULN if baseline value is normal > 3.0xbaseline value if baseline is abnormal
Albumin	g/dL	g/L	<2g/dL; <20g/L
Creatinine	mg/dL	μmol/L	>3.0x ULN
CRP ^a	mg/dL	mg/L	>10mg/dL >100 mg/L

Table 6-3: CTCAE v5.0 grades for laboratory assessments to be analyzed

Parameter	Unit (conventional)	Unit (Standard)	Marked Abnormality Criteria
Corrected Calcium (Ca) ^b	mg/dL	mmol/L	High: Corrected serum calcium of >12.5 mg/dL; >3.1 mmol/L Low: Corrected serum calcium of <7.0 mg/dL; <1.75 mmol/L
Potassium	mEq/L	mmol/L	Low: <3.0 mmol/L High: > 6.0 mmol/L
Sodium	mEq/L	mmol/L	Low: <125 mmol/L High: >155 mmol/L
Glucose ^c	mg/dL	mmol/L	Low: <40mg/dL; < 2.2 mmol/L High: >250 mg/dL; >13.9 mmol/L
eGFR ^d	mL/min/1.73 m ²	mL/min/1.73 m ²	eGFR <29 mL/min/1.73 m ²

^a Includes CRP and High Sensitivity (HS) CRP. Reference for marked abnormality criteria: Nehring, S.M.; Goyal, A.; Patel, B.C. (2020). StatPearls Publishing, web link: <https://www.ncbi.nlm.nih.gov/books/NBK441843/>

^b Corrected Ca (mg/dl) = Ca (mg/dl) + (0.8 [4 - measured albumin (g/dl)]); Corrected Ca = [0.8 x (normal albumin - patient's albumin)] + serum Ca, Karbhari, D.S.; Karbhari, S., Karbhari, N.S.; Patel, S. (2017).

^c Glucose high criterion defined by Grade 3 and higher events according to CTCAE, Version 4.03, June 14, 2010

^d GFR is calculated using the Chronic Kidney Disease Epidemiology Collaboration or CKD-EPI formula (https://qxmd.com/calculate/calculator_251/egfr-using-ckd-epi) which is eGFR = 141 * min(Scr/κ,1)α * max(Scr/κ, 1)-1.209 * 0.993Age * 1.018 [if female] * 1.159 [if black]; where Scr is serum creatinine (mg/dL), κ is 0.7 for females and 0.9 for males, α is -0.329 for females and -0.411 for males, min indicates the minimum of Scr/κ or 1, and max indicates the maximum of Scr/κ or 1. For derivation from values in standard units (umol/L) the κ values are 61.9 for females and 79.6 for males.

The table for the markedly abnormal liver function tests will contain data beyond the CTCAE v5.0 Grade 3 thresholds as outlined in **Table 6-4** above, in order to allow for a more thorough review of elevated liver function tests.

There will be one table by IMP in the SS, which will display the count and percentage of participants meeting the criteria mentioned in **Table 6-4** at any visit during the study (including unscheduled visits). For the combined criteria to be fulfilled the conditions should be present in the same visit.

The liver function results for study participants with markedly abnormal criteria will be listed for all study visits (that is including the not on treatment assessments).

Table 6-4: Markedly Abnormal Criteria for Liver Function Tests

Category	Parameter	Criterion ^a
Drug Hepatic disorders TEAEs	TEAEs in MedDRA SMQ	“Drug related hepatic disorders - comprehensive search (SMQ-narrow scope)” excluding the 2 sub-SMQs of “Liver neoplasms, benign (incl cysts and polyps) (SMQ)” and “Liver neoplasms, malignant and unspecified (SMQ)”
Elevated Liver Function Tests	AST	>3 x ULN, >5 x ULN, >8 x ULN, >10 x ULN, >20 x ULN
	ALT	>3 x ULN, >5 x ULN, >8 x ULN, >10 x ULN, >20 x ULN
	AST or ALT	>3 x ULN, >5 x ULN, >8 x ULN, >10 x ULN, >20 x ULN
	TBL	>1.5 x ULN, >2 x ULN
	ALP	1.5 x ULN
Potential drug-induced liver injury (DILI) criteria	AST or ALT	>3xULN with TBL >1.5xULN
	AST or ALT	>3xULN with TBL >2xULN
	Hy's Law	AST or ALT > 3×ULN with concurrent ALP < 2 × ULN and concurrent TBL > 2×ULN

^a Meeting the criteria at any post-baseline visit after the first infusion of study medication and within 40-days of the last injection and not meeting the same criteria during baseline

Criteria listed in [Table 6-5](#) will be applied in the determination of PCSA (Potentially Clinically Significant Abnormalities) in vital signs of the study participants.

Table 6-5: Abnormality Criteria in Vital Signs

Parameter	Criterion ^a
Systolic Blood Pressure (mmHg)	≤ 90 mmHg and a decrease from Baseline of ≥20 mmHg ≥ 160 mmHg and an increase from Baseline of ≥20 mmHg
Diastolic Blood Pressure (mmHg)	≤50 mmHg and a decrease from Baseline of ≥15 mmHg ≥105 mmHg and an increase from Baseline of ≥ 15 mmHg
Pulse rate (bpm)	≤50 mmHg and a decrease from Baseline of ≥15 mmHg ≥120 mmHg and an increase from Baseline of ≥15 mmHg

^a Meeting the criteria at any post-baseline visit after the first infusion of study medication and within 40-days of the last injection and not meeting the same criteria during baseline

Criteria listed in [Table 6-6](#) will be applied in the determination of abnormalities in ECG of the study participants.

Table 6-6: Abnormality Criteria in ECG

Parameter	Criterion ^a
QT interval (ms)	≥500ms; ≥60ms increase from Baseline

Parameter	Criterion ^a
QTc(F) (ms)	≥500ms; ≥60ms increase from Baseline
PR interval (ms)	Treatment-emergent value >200ms
QRS interval (ms)	Treatment-emergent value >100ms
Heart Rate (bpm)	<50bpm; >120bpm

^a Meeting the criteria at any post-baseline visit after the first infusion of study medication and within 40-days of the last injection and not meeting the same criteria during baseline

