4 POPULATIONS FOR ANALYSIS

- **Enrolled Set (ES):** will include in all screened participants including screen failures.
- **Intention-to-Treat Population (ITT):** will include all randomized participants.
- **ITT_{NoCOVID-19}:** will include all ITT participants excluding those with confirmed COVID-19 as observed during any visit of the Main Portion of the study and reported in the AE eCRF form.

Of note, ITT_{NoCOVID-19} will be considered in any analysis specified in the current document during the Main Portion only, provided it differs by at least 15% from the ITT in terms of number of participants.

- **Per Protocol Set (PPS):** will include all participants in the ITT Population who have completed the 8 Week Treatment Period and have no important protocol deviations. Important protocol deviations will be evaluated during ongoing data cleaning meetings prior to unblinding of the data.

If a participant received multiple doses of different study drug (i.e., placebo and 0.3 mg/kg), the patient will be assigned to the dose group which they received at the highest frequency within the Main Portion of the study.

- **Intention to Treat - Extension (ITT_{EXT}):** will include all participants who entered the Extension Portion of the study.
- **Safety Set (SS):** will include all participants who received at least 1 dose of study drug during the Main Portion of the study irrespective if they continued to the Extension Portion. Participants will be analyzed based on the actual treatment received.

If a study participant received multiple doses of different study drug (i.e., placebo and 0.3 mg/kg), the participant will be assigned to the dose group which he/she received at the highest frequency within the Main Portion of the study.

Of note, participants who were on placebo during the Main Portion of the study and continued to the Extension Portion will be included in both groups depending on the study period assessed. Safety results on 0.3 mg/kg across the Main and Extension Portions will be combined.

- **Safety Set No Covid-19 (SSNOCOVID-19):** will include all participants in the SS except those with confirmed COVID-19 (as reported in AE eCRF form) during any time of the study (Main or Extension Portion).
Of note, SSNOCOVID-19 will be considered in any analysis specified in the current document, provided it differs by at least 15% from the ITT in terms of number of participants.

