5.6.4.1.1 Laboratory values over time

All laboratory values listed at Table 5–1 of Section 5.6.4.1 will include on treatment data for analysis defined as the values after the first dose of the study drug until on or before the last dose plus 40 days (or last visit depending which occurs first). At all tables, laboratory assessments will be sorted by panel (chemistry, hematology, coagulation, urinalysis). Within each panel the assessments will be sorted alphabetically.

Summaries on Markedly Abnormal (MA) values will also be provided for the Main portion by scheduled visit and overall (including unscheduled visits) and for the Extension portion by scheduled visit and overall (including unscheduled visits), for each IMP. MA criteria are listed at Section 6.1.7, Table 6–3 MA criteria are defined by Grade 3 or higher events according to the Common Terminology for Adverse Events (CTCAE), Version 5.0, November 17, 2017 unless otherwise noted.

All laboratory test results will be listed, including baseline, scheduled and unscheduled visits with results in standard units. Values outside the reference range for the continuous variables will be flagged in the listings. The reference ranges will also be displayed. In addition, the

listings will include a flag for values identified as MA. Additional lab test for pregnancy testing, will also be listed.

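### Thirteen of the 18 parameters in SAP Table 6-3 have no baseline condition, so a laboratory abnormality that predates dosing and persists is counted as a post-baseline markedly abnormal value

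*SAP*

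**What the plan says.** SAP section 6.1.7 defines the laboratory rule for Table 6-3 as "The MA criterion is defined as the incidence of at least Grade 3 CTCAE, unless otherwise noted". The table has 18 parameters, and its rows are of two kinds.

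- **Baseline-relative (5 parameters).** AST, ALT and gamma-GT use ">5.0xULN if Baseline value is normal; > 5.0x Baseline value if Baseline is abnormal". ALP follows the same rule. Total bilirubin uses ">3.0xULN if baseline value is normal > 3.0xbaseline value if baseline is abnormal".
- **Fixed cut-off (13 parameters).** These are hemoglobin, WBC, lymphocytes, neutrophils, platelets, albumin, creatinine, CRP, corrected calcium, potassium, sodium, glucose and eGFR. The lymphocyte row, for example, reads "Low: <0.5 x 10 ⁹ /L High: >20 x 10 ⁹ /L".

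Footnote a to Tables 6-4, 6-5 and 6-6 (liver function tests, vital signs, ECG) limits the count to participants meeting the criterion after first dose "and not meeting the same criteria during baseline". Footnote a to Table 6-3 concerns CRP only, and its other footnotes cover calcium, glucose and eGFR.

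SAP section 5.6.4.1.1 restricts the laboratory data to values after first dose and then states: "Summaries on Markedly Abnormal (MA) values will also be provided for the Main portion by scheduled visit and overall". It plans the same for the Extension, for each IMP, and adds no baseline condition. SAP section 4 (Safety Set) assigns the treatment group by period: "participants who were on placebo during the Main Portion of the study and continued to the Extension Portion will be included in both groups". SAP section 5.1.1.2.4 makes the pre-dose Day E1 value the Extension baseline for those participants.

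**The concern.** A table of markedly abnormal values by treatment is read as what happened on treatment. For the 13 fixed-cut-off parameters it also contains what participants brought with them. Such values are plausible in some rows: participants continue stable corticosteroids and immunosuppressants (Protocol section 10.1.3), and no eligibility criterion sets a numeric limit on any of the 13 analytes.

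The gap looks like an omission. The other three tables in the section carry the condition, the TEAE definition in SAP section 5.6.2 requires worsening when an event was present at treatment start, and the Table 6-3 rule itself speaks of incidence. Because nothing implements that word, two programmers could produce different tables from the same text.

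At stake is the reading of small counts. One participant is 1/12 = 8.3 percentage points of an arm. In the Extension, a pre-existing abnormality in a former-placebo participant can only add to the zilucoplan count.

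**Working it through.** The plan states no figure for this point, so there is nothing to reproduce. The check has three steps.

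**1. Row count of Table 6-3.** There are 18 parameters. WBC, lymphocytes, calcium, potassium, sodium and glucose each have a high and a low criterion, which gives 18 + 6 = 24 criteria. Five parameters (5 criteria) refer to baseline, leaving 18 − 5 = 13 parameters and 24 − 5 = 19 criteria that do not.

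**2. Is an unchanged pre-dose abnormality flagged?**

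- AST at *b* × ULN, abnormal at baseline and unchanged: the rule needs *b* > 5*b*, which is impossible. At 3, 6 or 12 × ULN it is not flagged. ALT, ALP and gamma-GT behave the same way, as does bilirubin with 3 in place of 5.
- Lymphocytes at 0.4 × 10⁹/L before dosing and 0.4 afterwards: 0.4 < 0.5, so it is flagged at every visit where it persists. With the footnote of Tables 6-4 to 6-6 it would not be.

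Across the table, an unchanged abnormality is flagged for 13 of 18 parameters as written, and for 0 of 18 with the footnote.

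**3. Size for one criterion.** Inputs: 12 participants per arm (SAP section 1.2), an assumed prevalence *p* of meeting one fixed criterion before dosing, full persistence, no drug effect, and all 12 placebo participants entering the Extension. The last four are assumptions.

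Main Portion: X and Y are independent Binomial(12, *p*) counts with P(k) = C(12,k) *p*^k (1−*p*)^(12−k), and

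P(|X−Y| ≥ 2) = 1 − Σ P(k)² − 2 Σ P(k)P(k+1).

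For *p* = 0.05, P(0) to P(4) are 0.5404, 0.3413, 0.0988, 0.0173 and 0.0021. The sum of squares is 0.4186 and twice the sum of adjacent products is 0.4398, so the result is 1 − 0.8584 = 0.142.

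Extension: P(at least one carried over) = 1 − (1−*p*)^12, with expected number 12*p*.

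| Assumed *p* for one criterion | P(arms differ by ≥ 2) | Expected carry-over | P(≥ 1 carried over) |
|---|---|---|---|
| 1% | 1.1% | 0.12 | 1 − 0.8864 = 11.4% |
| 2% | 3.7% | 0.24 | 1 − 0.7847 = 21.5% |
| 5% | 14.2% | 0.60 | 1 − 0.5404 = 46.0% |

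The Main Portion figure is two-sided. By symmetry an excess of two or more on zilucoplan has half the probability: about 0.5%, 1.8% and 7.1%. With the footnote applied, all of these become zero.

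**The case against.** The case for leaving the table alone has several parts.

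- **Eligibility.** A reader might infer that nothing at entry restrains these analytes. That goes too far. Exclusion 11 (Protocol section 8.2) lets the investigator exclude for a significant laboratory abnormality, exclusion 2 removes current or recent systemic infection, and extension criterion 5 (Protocol section 8.3) is discretionary too. Many cut-offs are severe (hemoglobin below 8 g/dL, sodium below 125 mmol/L), where that judgement is likely to be used. This stands, and it supports low prevalences for most rows. It does not close the gap, because none of these limits is numeric.
- **Size.** Larger probabilities result if *p* is the chance of meeting any one of the fixed cut-offs: at 10% or 20%, arms of 12 differ by two or more with probability 29% or 44%. But SAP sections 5.6.4.1.1 and 6.1.7 specify no row that pools parameters, and high and low criteria are summarized separately. The single-criterion figures are the relevant ones.
- **Traceability.** SAP section 5.6.4.1.1 lists every laboratory result, baseline included, with a flag for markedly abnormal values. With about 24 participants a reader can find each pre-existing case. This stands. The shift tables in section 5.6.4.1.2 help less, because they use reference-range categories and not these cut-offs.
- **Labelling.** The SAP calls these summaries of values and does not label them treatment-emergent. A count of all values is a legitimate display, which is why the fix retains it.
- **Importance.** Laboratory change is listed under other safety endpoints (SAP Table 1-1) and is analysed descriptively. No hypothesis or decision rule depends on it. This stands and sets the severity.

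**Conclusion.** The inconsistency is real and limited to 13 of 18 parameters. For these, a persisting pre-dose abnormality is counted as a post-baseline markedly abnormal value, contrary to the rule used in the other three tables of the section.

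Three stronger readings might be inferred and are not supported:

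- **That the whole table is affected.** The five liver rows cannot flag an unchanged value. They include AST and ALT, which the SAP lists among the muscle enzymes (section 6.1.5.7) and which are therefore likely to be raised at entry. CK is not in the table.
- **That the Main Portion comparison is biased against zilucoplan.** Randomization leaves the over-count with no expected direction, so it is noise.
- **That a pooled table of these values transfers placebo findings to zilucoplan.** Main and Extension summaries are planned separately. SAP section 4 says 0.3 mg/kg safety results will be combined, but section 5.1.1.4 confines this to specific analyses and no pooled table of these values is named. The attribution arises in the Extension summaries through the group definitions, where there is no concurrent placebo group; the effect is to inflate a descriptive rate.

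The size rests on an unknown prevalence, full persistence and all 12 placebo participants continuing. At 1% to 5% for one criterion, it ranges from 1.1% to 14.2% for a Main Portion difference of two or more, and from 11.4% to 46.0% for at least one carried-over case. The point is minor.

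**What to change.** Add a footnote to the 13 fixed-cut-off parameters of Table 6-3 stating the condition already used in Tables 6-4 to 6-6: "and not meeting the same criteria during baseline". Define baseline as the pre-Day 1 value for the Main Portion and the Day E1 value for former-placebo participants in the Extension, as SAP section 5.1.1.2.4 already does. Participants randomized to zilucoplan keep their pre-Day 1 baseline throughout, so an abnormality that arose on drug in the Main Portion still counts later. Use as denominator the participants who did not meet the criterion at that baseline and have a post-baseline value.

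Keep the present all-values count as a second row, so that persistence or worsening in participants already abnormal at baseline stays visible.

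The cost is one footnote and one extra row per parameter in the summaries. No new data are needed and no efficacy analysis changes.
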